#### **4.2 Adverse Event Reporting and Monitoring**

##### **Adverse Event (AE)**

An Adverse Event (AE) is a subcategory of the broader category of "Unanticipated Problems Posing Risk to Subject or Others." An adverse event is defined as:

- Any unfavorable or unintended sign (including an abnormal laboratory finding), symptom, or disease occurring at any stage of the study
- Abnormal results of diagnostic procedures are considered to be adverse events if the abnormality:
  - results in study withdrawal
  - is associated with a serious adverse event
  - is associated with clinical signs or symptoms leads to additional treatment or to further diagnostic tests
  - is considered by the investigator to be of clinical significance
- May include an exacerbation of a pre-existing condition, intercurrent illness or injury, drug interaction, drug overdose, failure of expected action or significant worsening of the disease under study
- An event that may compromise the rights, safety, or welfare of research subjects

Any event that could be characterized by the definitions above is an AE whether or not considered related to the study or product.

### **Serious Adverse Event (SAE)**

Adverse events are classified as serious or non-serious. A ***serious adverse event*** is any AE that is:

- fatal
- life-threatening
- requires or prolongs hospital stay
- results in persistent or significant disability or incapacity
- a congenital anomaly or birth defect
- an important medical event

Important medical events are those that may not be immediately life threatening, but are clearly of major clinical significance. They may jeopardize the subject, and may require intervention to prevent one of the other serious outcomes noted above. For example, drug overdose or abuse, a seizure that did not result in in-patient hospitalization, or intensive treatment of bronchospasm in an emergency department would typically be considered serious.

All adverse events that do not meet any of the criteria for serious will be regarded as ***non-serious adverse events***.

### **Adverse Event Reporting Period**

The study period during which adverse events must be reported is the period from the initiation of any study procedures to the end of the study treatment follow-up. For this study, the study treatment follow-up is defined as 7 days following the last administration of study treatment. A compilation of any Adverse Events will be provided in the annual and final progress reports to NIDA.

### **Preexisting Condition**

A preexisting condition is one that is present at the start of the study. A preexisting condition will be recorded as an adverse event if the frequency, intensity, or the character of the condition worsens during the study period.

### **General Physical Examination Findings**

At screening, any clinically significant abnormality will be recorded as a preexisting condition. At the end of the study, any new clinically significant findings/abnormalities that meet the definition of an adverse event must also be recorded and documented as an adverse event.

### **Post-study Adverse Event**

All unresolved adverse events will be followed by the investigators until the events are resolved, the subject is lost to follow-up, or the adverse event is otherwise explained. At the last scheduled visit, a research team member will instruct

each subject to report any subsequent event(s) that the subject, or the subject's personal physician, believes might reasonably be related to participation in this study.

### **Hospitalization, Prolonged Hospitalization or Surgery**

Any adverse event that results in hospitalization or prolonged hospitalization will be documented and reported as a serious adverse event unless specifically instructed otherwise in this protocol. Any condition responsible for surgery should be documented as an adverse event if the condition meets the criteria for an adverse event.

Neither the condition, hospitalization, prolonged hospitalization, nor surgery are reported as an adverse event in the following circumstances:

- Hospitalization or prolonged hospitalization for diagnostic or elective surgical procedures for a preexisting condition. Surgery will **not** be reported as an outcome of an adverse event if the purpose of the surgery was elective or diagnostic and the outcome was uneventful.
- Hospitalization or prolonged hospitalization required to allow efficacy measurement for the study.
- Hospitalization or prolonged hospitalization for therapy of the target disease of the study, unless it is a worsening or increase in frequency of hospital admissions as judged by the clinical investigator.

Medical and scientific judgment should be exercised in deciding whether expedited reporting is appropriate in other situations, such as important medical events that may not be immediately life-threatening or result in death or hospitalization but may jeopardize the patient or may require intervention to prevent one of the other outcomes listed in the definition above. These should also usually be considered serious. Other kinds of events can be labeled "serious adverse events" at the discretion of the investigator.

To ensure no confusion or misunderstanding of the difference between the terms "serious" and "severe," which are not synonymous, the following note of clarification is provided: The term "severe" is often used to describe the intensity (severity) of a specific event (as in mild, moderate, or severe myocardial infarction); the event itself, however, may be of relatively minor medical significance (such as severe headache). This is not the same as "serious," which is based on patient/event outcome or action criteria usually associated with events that pose a threat to a patient's life or functioning. Seriousness (not severity) serves as a guide for defining regulatory reporting obligations.

### **Severity Grading Scale for Adverse Events**

Many disease specific groups have developed toxicity grading scales. For example, most cancer clinical trials use the Common Terminology Criteria for Adverse Events (CTCAE) developed by the NCI. The CTCAE provides a descriptive terminology which is utilized for adverse event reporting. A grading (severity) scale is provided for each adverse event term (<http://ctep.info.nih.gov>). If no guidelines exist, then the following scale can be used:

- Mild: Noticeable to the subject, does not interfere with the subject's daily activities, usually does not require additional therapy, dose reduction, or discontinuation of the study.
- Moderate: Interferes with the subject's daily activities, possibly requires additional therapy, but does not require discontinuation of the study.
- Severe: Severely limits the subject's daily activities and may require discontinuation of the study. This would include all adverse events defined as "serious adverse events".

### **Attribution/Association with the Drug or Intervention:**

An assessment of the relationship between the adverse event and the drug/intervention will be made for each occurrence by the Principal Investigator.

#### **Adverse Event Attribution Categories:**

- Unrelated - The AE is clearly NOT related to the intervention
- Possible - The AE may be related to the intervention
- Probably - The AE is likely related to the intervention
- Definitely - The AE is clearly related to the intervention

#### **4.3 Recording of Adverse Events**

At each contact with the subject after the Intake, the study research assistant will seek information on adverse events by specific questioning using a side effect checklist and, as appropriate, by examination. Side effects will be monitored through a two-pronged approach. First, participants will complete a side effects checklist (SEC) at each study visit after the Intake reporting with a frame of reference since their last study visit. The SEC will assess the frequency and severity of common side-effects associated with TN. These items will be rated by participants on a 0 (none) to 3 (severe) scale, and can be summed to provide an overall side effects index.

Second, trained staff will ask participants a non-structured, open-ended question (SEC Open-ended) at each study visit with a one-week frame of reference to assess if participants are experiencing any additional symptoms or medical concerns that may be related to their participation in the study.

Research staff are trained to inquire (time of onset, nature of issue reported, possible relation to transdermal nicotine treatment, review of previously reported side effects or concerns, etc.) about any notable side effects or medical concern reported by participants. Based on published reports using the 21, 14, and 7 mg doses of TN we expect few side effects and we expect these side effects to be mild and transient in nature. Any severe (or a pattern of moderate) side effects or notable medical concern will be treated as adverse events, and reported to the Study Physician to determine the severity of the AE, the relationship of the event to the study drug and decide the course of action for the study subject. This consult, including all relevant information, will be documented via email. The Study Physician is knowledgeable of side effects related to transdermal nicotine and is qualified to manage possible side effects. Mild side effects will not be reported as adverse events, but will be recorded and monitored by study staff.

All adverse events occurring during each study period will be recorded. The clinical course of each event will be followed until resolution, stabilization, or until it has been determined that the study treatment or participation is not the cause. Serious adverse events that are still ongoing at the end of the study period must be followed up to determine the final outcome. Any serious adverse event that occurs after the study period and is considered to be possibly related to the study treatment or study participation will be recorded and reported immediately.

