#### 2. Design

**Main Study.** This study will use a prospective observational matched-design to test whether HIV+ smokers (vs. HIV-smokers) are more likely to experience cognitive deficits during nicotine withdrawal and whether these deficits are predictive of smoking relapse. As shown in Figure 1, adult treatment-seeking smokers (N=300; 150 HIV+ and 150 HIV-) will complete this 12-week study, which is divided into two phases: a pre-quit laboratory phase (weeks 0-2) and a treatment phase (weeks 3-12). Subjects will complete two laboratory sessions during the pre-quit phase: once following 24 hours of mandatory smoking abstinence and once while smoking-as-usual (order counter-balanced; abstinence biochemically confirmed). A cognitive task battery assessing working memory, sustained attention, and response inhibition will be administered during each session. During the treatment phase, subjects will receive standard smoking cessation treatment, including six sessions of brief individual counseling (weeks 3-8) and eight weeks of open-label transdermal nicotine (TN) patch treatment (weeks 4-12) [34]. The primary outcomes will be: 1) cognitive performance (e.g., verbal and working memory) following 24-hours smoking abstinence (vs. smoking-as-usual) during the pre-quit phase, and 2) 7-day point-prevalence, biochemically confirmed abstinence rates at end-of-treatment (EOT) for the treatment phase. Since randomization is not possible in this study, we will rely on inclusion criteria and matching to reduce the potential for confounding. More specifically, participants will be

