#### **Behavioral Counseling (Week 3-Week 8).**

All subjects will receive manual-based counseling from a counselor trained and supervised by the PM or [name]. The counseling protocol is based on PHS guidelines for smoking cessation treatment (Fiore et al., 2008), used in our studies with smokers with HIV (IRB Protocol #815435), cancer patients (Schnoll et al., 2010a), and the general population of smokers (Schnoll et al., 2010b; R01 DA025078). Counseling is included given its efficacy at helping smokers quit (Fiore et al., 2008) and to increase study retention. The counseling sessions are designed to enhance awareness of the harmful effects of smoking, assist the person in developing skills to quit and avoid relapse, and instruct the smoker on TN use. Counseling is provided to all participants until Week 8. Counseling will be provided by phone or videoconference primarily, and counselors are not blind to participant group status. Sessions can be arranged at convenient times for the participants, including evenings.

**Pre-Quit Session (Week 3):** The counseling program begins at Week 3 with a 1-hour “pre-quit” counseling session to prepare for the target quit day. This session focuses on reviewing the participant’s history and experience with quitting as well as beliefs about smoking, quitting and perceived barriers to cessation. A quitting plan is initiated and involves identifying smoking triggers and strategies to increase the chance for success, including relying on social support to quit smoking and altering behaviors associated with smoking. TN will be mailed to the participant or dispensed prior to this session and the counselor will discuss the role of TN in withdrawal symptom management and provide directions on how to use TN.

**Target Quit Day Session (Week 4):** Participants will receive a 30-minute “quit-day” session to review the initial quit attempt, identify potential reasons for relapse, and review a plan for avoiding tempting situations. Adherence to nicotine patch use recommendations will be emphasized.

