**Relapse Prevention Sessions (Weeks 5-8):** Participants will then receive 4 additional 20-minute booster sessions at Weeks 5 through 8 which focus on either reinforcing success and reviewing the quit plan or reestablishing a quit date and restarting the cessation process. The counseling sessions are designed to enhance awareness of the harmful effects of smoking, assist the person in developing skills to quit and avoid relapse, and instruct the smoker on varenicline use.

**Cardio monitoring sub-study only:** At Week 8 participants may have the non-invasive rhythm monitoring device applied by trained research staff. If necessary, they may be mailed the device and a staff member will contact them to walk through the application remotely. The application will be identical to the one at Lab session 2. Participants will be instructed to wear the device for two weeks after which time they will return the device using the study provided pre-paid envelope.

All counseling sessions may be audio-taped and a random 15% of sessions will be assessed for protocol adherence.

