#### **Transdermal Nicotine (Weeks 4-12).**

All participants will receive transdermal nicotine (TN) to aid in quitting smoking. TN is available over the counter and is very well tolerated. Participants will use “the patch” in a tapering fashion as recommended by the manufacturer. Participants who smoke 10 or more cigarettes per day will adhere to the following dosing guidelines: 21 mg for 4 weeks; 14 mg for 2 weeks and 7 mg for 2 weeks. Participants who smoke between 5 and 9 cigarettes per day will follow a modified

dosing regimen: 14 mg for 6 weeks and 7 mg for 2 weeks. Participants who smoke between 1 and 4 cigarettes per day will also follow a modified dosing regimen: 7 mg for the full 8-week schedule. The 8-week regimen will commence the morning of the 2nd counseling session (**week 4; TQD**). Participants will be instructed not to smoke beginning that morning and apply a patch. Directions and rationale for use will be discussed during the pre-quit counseling session (**week 3**). Use is reviewed at every post-TQD session and TN will be distributed weekly. If a participant does not have enough patches to continue with their treatment schedule (e.g., used two patches in one day should one fall off), additional supplies of nicotine patches may be mailed or picked up by the participant, if appropriate.

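### The open-ended adverse-event question looks back one week, but visits jump from week 8 to week 12, leaving 3 of the 8 patch weeks outside its stated window

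*Combined protocol and SAP*

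**What the plan says.** Section 4.3 (Recording of Adverse Events) describes two scheduled instruments with different recall periods.

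- **Checklist.** Participants complete a "side effects checklist (SEC) at each study visit after the Intake reporting with a frame of reference since their last study visit". Its scope is limited: "The SEC will assess the frequency and severity of common side-effects associated with TN".
- **Open-ended question.** Staff ask an "open-ended question (SEC Open-ended) at each study visit with a one-week frame of reference", to pick up further symptoms or medical concerns that may be related to participation.

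The same section then states: "All adverse events occurring during each study period will be recorded". The section on the Adverse Event Reporting Period runs that duty from the first study procedure to 7 days after the last study treatment.

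On timing, section 2 (Design) gives "eight weeks of open-label transdermal nicotine (TN) patch treatment (weeks 4-12"). The counselling section schedules "4 additional 20-minute booster sessions at Weeks 5 through 8" and says "Counseling is provided to all participants until Week 8". The next visit is the end-of-treatment visit at week 12. Neither Table 1 nor the table under Subject Compensation lists anything between weeks 8 and 12.

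The Side Effects paragraph under Treatment Measures mentions the open-ended question without a time frame, so nothing there changes the one-week frame.

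**The concern.** The open-ended question is the scheduled enquiry meant for events that are not on the patch checklist. A one-week look-back is complete while visits are a week apart. It is not complete across the four-week interval that ends treatment, and a missed weekly visit opens the same kind of gap.

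What is at stake is the completeness of the adverse-event record, which is compiled for the funder in annual and final reports. The protocol expects side effects to be mild and transient. An unlisted event that comes and goes between weeks 8 and 11 is the kind that a one-week question at week 12 does not reach.

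**Working it through.** **Inputs**

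- Patch period: weeks 4 to 12 (section 2, Design; Transdermal Nicotine).
- Visits after the target quit day: weeks 5, 6, 7, 8 and 12 (Behavioral Counseling; End of Treatment Follow-up Visit; Table 1).
- Look-back: 1 week for the open-ended question, since the last visit for the checklist (section 4.3).

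**Step 1: reproduce the length of treatment.** 12 − 4 = 8 weeks = 56 days. The two stepped patch schedules give the same total: 4 + 2 + 2 = 8 and 6 + 2 = 8.

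**Step 2: mark each patch week covered if it falls within a visit's one-week look-back.**

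| Patch week | Visit whose one-week look-back covers it |
|---|---|
| 4–5 | week 5 |
| 5–6 | week 6 |
| 6–7 | week 7 |
| 7–8 | week 8 |
| 8–9 | none |
| 9–10 | none |
| 10–11 | none |
| 11–12 | week 12 |

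Covered: 5 × 7 = 35 days. Uncovered: 56 − 35 = 21 days. 21/56 = 37.5% of treatment. Of the 28 days after week 8, 21/28 = 75% are uncovered.

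**Step 3: vary the attendance.**

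- Final visit held at week 13: 4 of 8 patch weeks uncovered.
- Final visit held at week 11: still 3 of 8.
- One visit missed among weeks 5 to 8, all else on time: 21 + 7 = 28 days, and 28/56 = 50%.

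**Step 4: apply the checklist's frame to the open-ended question.** With visits on schedule, the week-12 question reaches back to week 8 and 0 of 8 patch weeks are uncovered.

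**The case against.** The strongest reply is that the remaining loss is narrow.

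- **Listed effects have no gap.** The checklist runs since the last visit, so the commonly expected patch effects are asked about throughout. This stands.
- **Continuing events are caught.** An unlisted event that starts in weeks 8 to 11 and lasts into the final week falls within the week-12 question. This stands.
- **Other routes exist.** Medications are reviewed at week 12, which may reveal a treated event. Participants can reach staff at any hour and are told in writing to call about severe side effects or adverse events. Staff are trained to ask about onset once something is mentioned. All true, but the first route is indirect, the second depends on the participant, and the third needs a prior disclosure.
- **Contacts between visits.** Section 4.3 has staff seek adverse events at each contact, and patches are said to be distributed weekly, so contacts in weeks 9 to 11 are plausible. However, that sentence names the checklist and examination, not the open-ended question. Patches may also be mailed, and no session is scheduled in those weeks.
- **Not every symptom counts.** Under section 4.3, severe side effects, a pattern of moderate ones, or a notable medical concern are treated as adverse events. An isolated moderate side effect that resolved would not necessarily enter the compilation even if elicited. This stands.
- **The form is not in the documents.** The case report forms and Manual of Operations may word the question differently. This limits certainty about practice, not about what section 4.3 says.

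A reader might go further and infer that events in weeks 8 to 11 cannot be reported at all, or that 37.5% of adverse events are lost. The routes above rule out the first, and the second confuses days with events. A reader might also infer that later treatment will be made to look safer than earlier treatment, or that the HIV groups will be biased apart. The analysis plan contains no early-versus-late safety comparison, and both groups follow the same visit schedule.

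**Conclusion.** The concern holds as an inconsistency within section 4.3, and between that section's one-week frame and the duty to record all adverse events. With the frame applied literally, visits on schedule and patches started at the week-4 session, 3 of 8 patch weeks (21 of 56 days) lie outside any scheduled open-ended look-back.

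What can be missed is an event that meets four conditions: it is not on the checklist, it has resolved before about week 11, the participant does not volunteer it, and the medication review does not reveal it. The direction is towards under-recording of such events after week 8. Their number cannot be estimated from the documents. Cognition and abstinence, the primary outcomes, are unaffected. The change should be made because it improves safety capture at almost no cost, not because the trial's main conclusions depend on it.

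**What to change.** In section 4.3 and on the form, change the open-ended question's frame of reference from one week to the time since the participant's last completed study visit. Add the same time frame to the Side Effects paragraph under Treatment Measures, which gives none. Referring to the last completed visit also covers gaps left by missed sessions, once the participant attends again.

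The cost is a wording change in the protocol and the form; no visit, staff time or instrument is added. The downside is that four-week recall at week 12 is less exact than one-week recall, which the plan already accepts for the checklist.

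### The adverse event definition has no severity threshold, but the recording rule keeps mild side effects out of adverse event reporting, so the safety summaries would cover only a severity-restricted subset

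*Combined protocol and SAP*

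**What the plan says.** All the text is in the Data and Safety Monitoring part of the combined protocol and SAP.

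- **Definition (4.2, Adverse Event).** The first limb is "Any unfavorable or unintended sign (including an abnormal laboratory finding), symptom, or disease occurring at any stage of the study". The section closes with "Any event that could be characterized by the definitions above is an AE whether or not considered related to the study or product". Neither sentence sets a minimum severity.
- **Grading (Severity Grading Scale for Adverse Events).** The lowest grade reads "Mild: Noticeable to the subject, does not interfere with the subject's daily activities, usually does not require additional therapy". The scale is offered as a fallback where no other grading guideline applies.
- **Operating rule (4.3, Recording of Adverse Events).** "Any severe (or a pattern of moderate) side effects or notable medical concern will be treated as adverse events", and these go to the Study Physician. The same paragraph ends "Mild side effects will not be reported as adverse events, but will be recorded and monitored by study staff".
- **Completeness (4.3).** "All adverse events occurring during each study period will be recorded".
- **Outputs.** Adverse Event Reporting Period promises the funder a compilation of AEs with the annual and final reports. The reporting period starts with the first study procedure and ends 7 days after the last study treatment. The Data, Safety and Monitoring Report, prepared yearly, includes a summary of AEs and serious AEs.
- **Data collection (Side Effects; 4.3).** Participants rate common patch side effects from 0 (none) to 3 (severe) on a checklist, and staff ask an open-ended question.

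**The concern.** Section 4.3 lets one rule do two jobs. Deciding when the Study Physician must look at an event is an escalation question. Deciding whether the event is an AE is a counting question, which section 4.2 has already answered without reference to severity. When the escalation threshold also decides what is an AE, the compilation and the annual summary no longer count what the protocol says an AE is.

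Three things follow.

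- Section 4.3 itself expects side effects to be few, mild and transient, so the class left out is the one the protocol expects to be most common.
- The relationship to treatment is to be assessed for each AE (Attribution/Association with the Drug or Intervention). An event never classed as an AE need not receive that assessment.
- Other Reportable events treats a side effect that proves more frequent than expected as reportable. An AE count without mild events is a poor basis for that check unless someone also consults the checklist.

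The protocol does not define what makes a pattern or what makes a concern notable. Inclusion of moderate events could therefore vary between staff members and over the 63 months of accrual.

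**Working it through.** No sample size, power or event figure enters this point, so the check sets the definition against the operating rule, one class of event at a time.

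| Class of event | AE under the 4.2 definition? | AE under the 4.3 rule? |
|---|---|---|
| Severe side effect | Yes | Yes |
| Moderate side effect forming part of a pattern | Yes | Yes |
| Any side effect judged a notable medical concern | Yes | Yes, by that route |
| Isolated moderate side effect, not judged notable | Yes | No, by implication |
| Mild side effect, not judged notable | Yes | No, stated outright |

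The two columns differ in the last two rows. A mild side effect is an unfavourable symptom, so it falls inside the definition, and the Mild grade confirms that such events were meant to be graded as AEs. The second column is therefore a proper subset of the first, cut by severity.

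Some events reach the AE listing by other routes, whatever the side-effect rule says. These are qualifying abnormal diagnostic results (4.2), worsened pre-existing conditions, new findings at the end of the study, and conditions leading to surgery, the last three under their own subheadings. They do not bring back the last two rows.

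The sentence on completeness does not settle the matter. Mild effects are recorded, but as side effects rather than AEs, so staff could satisfy that sentence and still produce the narrower listing.

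To size the shortfall one would need the number of mild events and of isolated moderate events not judged notable. The documents give no expected AE rate and no count by grade, so no figure or range can be derived.

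A secondary wording point concerns serious and severe. The Hospitalization subsection says that the two terms differ in meaning and that "Seriousness (not severity) serves as a guide for defining regulatory reporting obligations". The Severe grade then says "This would include all adverse events defined as" serious. An event of low intensity that prolonged a hospital stay would be graded Severe under that sentence.

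**The case against.** The strongest reply is that nothing is lost. The sentence that withholds the AE label from mild effects also says that staff record and monitor them, and the checklist holds a 0-to-3 rating for every participant. On this view section 4.3 only decides what is forwarded to the physician. The first part stands: the data exist. The second does not fit the text, because 4.3 says which side effects are treated as AEs, not merely which are passed on, and the promised compilation and summary are of AEs.

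A reader might infer several stronger claims that the documents do not support.

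- *That a mild AE cannot exist.* The notable-concern route has no severity threshold, the Study Physician grades severity after an event has been classed as an AE, and several sections admit AEs from outside the checklist.
- *That a single moderate event never counts.* Its exclusion is inferred from the word pattern, and the notable-concern route remains open to it.
- *That a planned analysis of AE rates, or of patch tolerability in HIV+ against HIV- smokers, is spoiled.* The statistical sections plan neither, and checklist scores could be tabulated by group under the present text.
- *That only one severity level in three counts, as if that were a share of events.* This restates the rule. The documents anchor only the ends of the checklist scale and give no distribution of scores.
- *That the serious and severe passages flatly contradict each other.* Placing serious events inside Severe is a one-way inclusion within a fallback scale. A severe event can still be non-serious.

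**Conclusion.** Wrong as written, at low severity. The definition and the operating rule identify different sets of events, and no other section reconciles them. Unless the text is changed, the AE compilation to the funder and the AE summary in the annual report will present a severity-restricted subset under the label of all AEs. The direction of the effect is certain: fewer events, with the gap at the mild end and, by implication, among isolated moderate events. Its size cannot be derived.

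The conclusion assumes that staff follow section 4.3 when compiling AEs, since it is the operating instruction. If they follow section 4.2 instead, the counts would be right and the clause on mild effects would be disregarded. Either way the sections need to be reconciled. Neither the cognitive outcomes nor abstinence at end of treatment is touched.

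**What to change.** Separate counting from escalation, and bring section 4.2 and both statements in section 4.3 into line.

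1. Apply the section 4.2 definition to all events at any severity, over the whole stated reporting period starting with the first study procedure. A count limited to events new or worse since the last visit before patch use would not do. It would miss events confined to the blood draw and the laboratory phase, and so would create a fresh mismatch.
2. Tabulate these events by grade and HIV group in the AE compilation and in the annual safety summary.
3. Remove the clause in 4.3 that keeps mild side effects from being reported as AEs.
4. Leave the existing trigger for physician review unchanged, including its notable-medical-concern limb.

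If the sponsor prefers the restricted listing, say in Adverse Event Reporting Period and in the Data, Safety and Monitoring Report that it is restricted by severity, and report the checklist data by grade and HIV group beside it.

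As a minor edit, reconcile the sentence that places all serious events in Severe with the clarification under Hospitalization.

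The cost is protocol wording, a table built largely from data already collected, and a longer AE listing. One thing to check first: the text puts the checklist at every visit after Intake, whereas Table 1 as extracted seems to start it at the quit-day session. The column alignment may be damaged, so the source table should settle whether the laboratory visits are covered.
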